### **6.3.Secondary endpoints**

- Change in SARS-CoV-2 viral load from baseline (day -1 or day 1 before administration of the study drug) measured at days , 4, 7, 15 and 31.
- Time until the detection of COVID-19 by PCR obtained from nasopharyngeal exudate or sample from the lower respiratory tract compared to baseline (day -2 or -1 or day 1 before administration of the study drug).
- Mortality at 7, 15 and 31 days.
- Percentage of patients requiring invasive mechanical ventilation and/or ICU admission at 7, 15 and 31 days.
- Percentage of patients requiring non-invasive mechanical ventilation at 7, 15 and 31 days.
- Percentage of patients requiring oxygen therapy at 7, 15 and 31 days.
- The recommended dose level will be selected after the joint evaluation of the safety and efficacy data obtained in this study between the sponsor and the Spanish Agency of Medicines and Medical Devices.

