### **7.1. Inclusion criteria**

1. Patient who agrees to participate in the study by signing the informed consent.
2. Men and women (non-pregnant) aged  $\geq 18$  years.
3. PCR-confirmed COVID-19 infection obtained from nasopharyngeal exudate or sample from the lower respiratory tract.
4. Patients who require hospitalisation for COVID-19
5. Onset of symptoms no later than 10 days prior to study inclusion.
6. Men and women with reproductive capacity must agree to use highly effective contraceptive methods (diaphragm plus spermicide or male condom plus spermicide, oral contraceptive combined with a second method of contraceptive implant, injectable contraceptive, permanent intrauterine device, sexual abstinence or vasectomy) during their participation in the study and in the 6 months following the last administration of plitidepsin.
7. In addition, women participating in the study with reproductive capacity must have a negative pregnancy test at enrolment.

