  - 9 The first time the patient tested positive for COVID-19 will be included as well. The test will be repeated in the 48 hours prior to administration of plitidepsin and on days 4, 7, 15 and 31, if negative detection does not occur before then. Qualitative PCR shall be obtained on nasopharyngeal exudate (preferably) or a sample from the lower respiratory tract.
  - 10 A chest X-ray will be performed at baseline and subsequently based on clinical discretion.
  - 11 Only fertile women.
  - 12 Patients may receive other pharmacological treatments for COVID-19 at the discretion of the investigator 24 hours after administration of the last dose of plitidepsin.
  - 13 Adverse events (serious and non-serious) will be recorded from signing of the informed consent up to 28 days after administration of the last dose of plitidepsin.
  - 14 A safety visit will be made 28 days (+3 days) after the last dose of plitidepsin.
  - 15 The viral load should be determined in a sample obtained from nasopharyngeal exudate (preferably) or a sample from the lower respiratory tract.

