2.6 Endpoints

Primary endpoints:

To set the safety and toxicological profile of plitidepsin at each dose level administered in patients admitted for COVID-19, the following variables will be analyzed:

- Occurrence frequency of the following grade ≥ 3 adverse events according to the NCI-CTCAE criteria v5.0 at 3, 7, 15 and 31 days:
 - Hematological
 - Neutropenia
 - Thrombocytopenia
 - Anemia
 - Lymphopenia
 - Non hematological
 - CPK increase
 - ALT and/or AST increase
 - Total bilirubin increase or direct bilirubin

- Neurotoxicity
- QT-QTc interval prolongation
- Other grade ≥ 3 adverse events
- Percentage of patients with uncompleted treatment and the reasons.
- Percentage of patients with AEs and SAEs at days 3, 7, 15 and 31.
- Changes from baseline (day -1 or day 1 before administration of study medication) in hematological and non-hematological parameters on days 3, 7, 15, 31.
- Percentage of patients with ECG abnormalities at days 2, 3, 4, 5, 6, 7, 15 and 31.

Secondary endpoints:

- Change from baseline in SARS-CoV-2 viral load (day -1 or day 1 before administration of study medication) measured at 3, 4, 7, 15, and 31 days.
- Time to negative detection of SARS-CoV-2 by PCR obtained in nasopharyngeal swab or sample from the lower respiratory tract compared to baseline (day -2 or -1 or day 1 before administration of study medication).
- Deaths at 7, 15 and 31 days.
- Percentage of patients that need for invasive mechanical ventilation at 7, 15, and 31 days.
- Percentage of patients that need for non-invasive mechanical ventilation at 7, 15, and 31 days.
- Percentage of patients that need for oxygen therapy at 7, 15 y 31 days.
- The recommended dose level will be selected after the evaluation of the safety and efficacy data obtained in this study between the sponsor and the Spanish Agency for Medicines and Health Products.

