APPENDIX III

12 EFFICACY EVALUATION

12.1 Efficacy evaluation

Table 12.1.1 Number of patients with PCR

Number of patients with PCR	Dose Cohort			
	1.5 mg N=X	2.0 mg N=X	2.5 mg N=X	Total N=X
Baseline				
Undetectable				
Positive				
Day ...				

Table 12.1.2 Viral load classification by dose level and total

Day	Viral Load at baseline (copies/mL)	Viral Load classification during treatment (copies/mL)			
		Low <4	Medium [4-7]	High >7	Total
Day 4	Low <4				
	Medium [4-7]				
	High >7				
	Total				
...(*)	Low <4				
	Medium [4-7]				
	High >7				
	Total				

(*) Days 7, 15 and 31

Listing 12.1.3 Viral load evolution

Subject id	Dose	Visit	Result	log10 viral load copies/mL

Table 12.1.4 Summary of Protocol-Specified Efficacy Endpoints. Cumulative results.

Endpoint from day 1 to	Dose Cohort			
	1.5 mg N=X	2.0 mg N=X	2.5 mg N=X	Total N=X
Patients discharged from hospital, n (%)				
Day 7				
Day 8				
Day 15				
Day 31				
Deaths at, n (%)				
Day 7				
Day 15				
Day 31				
Later than Day 31				
Patients requiring invasive mechanical ventilation and/or ICU admission at, n (%)				
Day 7				
Day 15				
Day 31				
Patients requiring invasive mechanical ventilation, n (%)				
Day 7				
Day 15				
Day 31				
Patients requiring ICU admission at, n (%)				
Day 7				
Day 15				
Day 31				
Patients requiring non-invasive mechanical ventilation at, n (%)				
Day 7				
Day 15				
Day 31				
Patients requiring oxygen therapy at, n (%)				
Day 7				
Day 15				
Day 31				
Patients requiring oxygen therapy (high flow) at, n (%)				
Day 7				
Day 15				
Day 31				
Patients requiring oxygen therapy (low flow) at, n (%)				
Day 7				
Day 15				
Day 31				

This table will be also performed by age (<65 vs. ≥65 year old (12.1.4.1)

This table will be also performed by FDA classification (12.1.4.2)

Table 12.1.5 Summary of Protocol-Specified Efficacy Endpoints. Non-cumulative results.

Endpoint	Dose Cohort			
	1.5 mg N=X	2.0 mg N=X	2.5 mg N=X	Total N=X
Patients discharged from hospital, n (%)				
Day 1 to Day 8				
Day 9 to Day 15				
Day 16 to Day 31				
Deaths at, n (%)				
Day 1 to Day 7				
Day 8 to Day 15				
Day 16 to Day 31				
Later than Day 31				
Patients requiring invasive mechanical ventilation and/or ICU admission at, n (%)				
Day 1 to Day 7				
Day 8 to Day 15				
Day 16 to Day 31				
Patients requiring invasive mechanical ventilation, n (%)				
Day 1 to Day 7				
Day 8 to Day 15				
Day 16 to Day 31				
Patients requiring ICU admission at, n (%)				

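### Viral-load and PCR samples may come from different airway sites at different visits, and the SAP neither lists specimen type nor checks what a switch does to change from baseline or time to negative

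*Protocol*

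**What the plan says.** **Sampling.** In Protocol section 10, footnote 15 covers viral load: "The viral load should be determined in a sample obtained from nasopharyngeal exudate (preferably) or a sample from the lower respiratory tract". Footnote 9 covers the qualitative test: "Qualitative PCR shall be obtained on nasopharyngeal exudate (preferably) or a sample from the lower respiratory tract". Nasopharyngeal is the preferred site in both, and the choice is open at each sampling day (baseline and days 4, 7, 15 and 31). Footnote 9 repeats the PCR on the later days only "if negative detection does not occur before then".

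**Entry.** Protocol 7.1 accepts either site with no preference: "PCR-confirmed COVID-19 infection obtained from nasopharyngeal exudate or sample from the lower respiratory tract". Exclusion criterion 5 in Protocol 7.2 bars patients on invasive or non-invasive ventilation at inclusion.

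**Endpoints.** Protocol 6.3 lists "Change in SARS-CoV-2 viral load from baseline" without naming a specimen. SAP 2.6 accepts either site for the second virological endpoint: "Time to negative detection of SARS-CoV-2 by PCR obtained in nasopharyngeal swab or sample from the lower respiratory tract compared to baseline".

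**Analysis.** SAP 8.1 a) analyses mean change in log10 copies/mL, direction of change against the previous visit, and undetectable load by day. SAP 8.1 c) analyses time to negative by Kaplan-Meier. It counts the first negative if the next PCR is not positive, or a negative at the last PCR (Day 31). None of these is restricted to, stratified by or checked against specimen type. Listing 12.1.3, "Viral load evolution", has columns for subject, dose, visit, result and log10 value only.

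**The concern.** A change from baseline is a within-patient contrast, and it assumes that both values measure the same thing. A nasopharyngeal swab and a lower-airway sample need not give the same copies/mL in the same patient on the same day. If the site changes between visits, the difference between sites is added to the difference over time, and the two cannot be separated. Likewise, a negative result from one site does not show clearance at the other.

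Switching is also unlikely to be random. Ventilated patients are excluded at entry, so intubation can happen only after baseline. Where it makes a lower-airway sample convenient, the specimen changes because the patient has worsened. SAP Appendix V then compares viral-load curves between good and poor outcomes, with poor meaning death or no discharge before day 9. Intubated patients would be expected mostly in the poor group, so a specimen effect there could be read as slower or faster viral decline.

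Viral-load change is the first efficacy measure in the secondary objectives, and the efficacy data enter the joint sponsor and agency decision on dose.

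**Working it through.** The plan gives no figure to reproduce: it states no between-specimen difference, standard deviation, effect size or power for viral load. The check has a textual part and an illustration of size.

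**1. Is a switch prevented, visible or handled?**

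- *Prevented:* no. Footnotes 9 and 15 state a preference, not a rule to keep the same site within a patient, and no other section adds one.
- *Visible in the planned listing:* no. Listing 12.1.3 has no specimen column.
- *Handled in the analysis:* no. SAP 8.1 a) to c) sets no same-specimen condition and no sensitivity analysis.
- *Standardised elsewhere:* only on the assay side. Captions of the viral-load figures in SAP 12.1 refer to a central laboratory, which does not fix where the sample is taken.

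**2. How far is time to negative protected?**

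SAP 8.1 c) cancels a negative if the following PCR is positive, so a negative caused by a switch would be caught if a further PCR were taken. Footnote 9 makes that further PCR conditional on no earlier negative, so it may never be taken. Viral-load sampling under footnote 15 carries no such condition, but the event in SAP 8.1 c) is defined on PCR. Protocol 12.5.1 is looser still and takes the first negative PCR date. One artefactual event is 1/15 = 6.7% of an arm.

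**3. Size for one patient.**

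Assume that specimens differ by d = 0.5 to 1.5 log10 copies/mL (not in the documents) and that the true fall is 2 log10 (illustrative). After a switch the observed fall is 2 − d or 2 + d:

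- 2 − 1.5 = 0.5 to 2 − 0.5 = 1.5, or
- 2 + 0.5 = 2.5 to 2 + 1.5 = 3.5.

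**4. Size for an arm.**

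The planned n is 15 per dose level (Protocol 6.1). If k patients switch in the same direction, the mean change shifts by k × d / n. With k = 2 (assumed):

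- 2 × 0.5 / 15 = 0.07 log10
- 2 × 1.5 / 15 = 0.20 log10

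With k = 0 the shift is zero. Two switches of equal size in opposite directions cancel. With fewer than 15 evaluable pairs, the same switches weigh more.

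**5. Chance that it arises at all.**

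For an assumed per-patient switching probability p, the chance of at least one switch in an arm of 15 is 1 − (1 − p)^15:

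| p | Chance of at least one switch |
|---|---|
| 0.02 | 0.261 |
| 0.05 | 0.537 |
| 0.10 | 0.794 |
| 0.20 | 0.965 |

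The documents give no value of p. Protocol 5.2 cites close to 10% of patients in Madrid needing mechanical ventilation. That is at best a loose guide, because it describes a different population and not every ventilated patient would switch.

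**The case against.** The case for leaving the plan alone has five parts.

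**The default already works.** Nasopharyngeal sampling is preferred in both footnotes, and ventilated patients are excluded at entry, so lower-airway baselines should be uncommon. This stands. It makes a switch from swab to lower airway after intubation the realistic route and the reverse switch unlikely. It does not bar either.

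**The SAP confirms negatives.** A reader might infer that any first negative counts as an event whatever follows. SAP 8.1 c) does not say that. The protection is real but incomplete, for the reason in step 2 of the working.

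**A switch may be traceable.** A reader might infer that it could never be detected. The documents do not support that: Listing 12.1.3 is a shell and the eCRF is not included, so specimen type may be captured somewhere. What can be said is that the planned outputs do not show it. Nor do the documents support an inference that switching would differ between sites.

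**The size is assumption.** This also stands. The specimen difference, the number of switchers and their common direction are all assumed, and 0.07 to 0.20 log10 is small against an illustrative fall of 2 log10. For the individual patient who switches, however, the recorded change has no clear meaning whatever happens to the mean.

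**Removing mismatched samples could do harm.** A natural remedy would be to treat them as not available. SAP 4.6 plans no imputation, so this would delete values mainly from patients who had worsened and could flatter the result. The objection is sound, and it is why the fix below keeps those values in the main analysis.

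**Conclusion.** The gap is real and worth closing. The plan lets a patient's specimen type change between visits, and the SAP neither lists specimen type nor examines its effect. For a patient who switches, log10 change from baseline is not comparable with that of patients who do not, and a negative PCR need not mean clearance at the baseline site.

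The documents support no more than that. They do not show that any switch took place, how large the specimen difference is, or in which direction it would act. A reader might infer that the viral-load results are biased or that the dose choice is undermined; neither follows. On the stated assumptions (0.5 to 1.5 log10 between specimens, 2 of 15 switching the same way) the arm's mean change moves by 0.07 to 0.20 log10, and by zero if nobody switches.

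The endpoints affected are secondary and the analyses descriptive. The primary safety objective is untouched, and dose selection has no viral-load threshold that such a shift could cross. The point still merits a change, because viral load feeds that selection and the change is cheap.

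**What to change.** **Protocol section 10, footnotes 9 and 15.** Require the same specimen type as that patient's baseline at every visit, with nasopharyngeal as the default.

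**Data capture and listing.** Record specimen type at each viral-load and PCR sample, and add it as a column to Listing 12.1.3.

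**SAP 8.1 a) to c).** Keep the all-specimen analysis. Add a sensitivity analysis of change from baseline and time to negative restricted to results from the same specimen type as baseline. Report the number of mismatched samples by arm, and state that excluding them may be informative because a switch is most plausible after worsening.

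If sampling is already complete, the listing column and the sensitivity analysis can still be done wherever specimen type is in the source records.

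**Cost.** One sentence in each footnote, one extra data field and one extra analysis, with no added visit. The restricted analysis will rest on fewer values and should be read beside the all-specimen one.

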## **11. ADVERSE EVENTS**

Safety information in clinical studies must be collected efficiently and consistently. Adverse events should be identified and reported promptly, so that potential risks to patients can be determined and regulatory requirements for reporting of adverse events can be met.

### **11.1. Definitions**

#### **11.1.1 Adverse Event (AE)**

An AE is any undesirable event that occurs to a patient undergoing clinical research, temporarily associated with the use of a drug, whether or not it is deemed to be related to the investigational products. Therefore, an adverse event can be any unintended and unfavourable sign (including an abnormal analytical result), symptom or disease that is temporarily associated with the use of a drug, whether or not it is deemed to be related to it. Pre-existing conditions that worsen during the study will be reported as Adverse Events.

AEs include pre or post-treatment events that occur as a consequence of study procedures (e.g. invasive procedures or modification of the patient's previous medication).

#### **11.1.2 Serious Adverse Event (SAE)**

An SAE is an undesirable medical event that, at any dosage:

- Causes death.
- Is life-threatening (NOTE: The term "life-threatening" refers to the investigator's judgement that the patient is at risk of death as a consequence of said event. However, this term does not refer to the fact that if the AE had been more intense, it would have placed the patient at imminent risk of death).
- Causes hospitalisation or prolongs a previous hospitalisation (NOTE: Hospitalisation is generally understood to mean that the patient has stayed in the hospital or emergency department for at least 24 hours. Complications that occur during hospitalisation are AEs. If a complication prolongs hospitalisation or meets any of the other severity criteria, then the event will be considered an SAE. When in doubt as to whether or not "hospitalisation" has occurred, the AE will be considered serious. Hospitalisation to carry out a scheduled treatment of a disease prior to the subject entering the study and that has not worsened with respect to their baseline situation is not considered an SAE). Hospitalisation due to social reasons is not considered an AE.
- Causes impairment or disability (NOTE: Impairment involves significant impact on a person's ability to carry out their daily tasks, but not that caused by minor medical conditions such as headaches, nausea, vomiting, diarrhoea, influenza or

accidental trauma (such as a ankle sprain), which can hinder or interfere with activities of daily living, but do not significantly impair them).

- Results in a congenital anomaly or birth defect.
- Is medically important (that is, a medically important adverse event may not be immediately life-threatening or result in immediate hospitalisation or death. However, if it is determined that the event may harm the patient and/or may require intervention to prevent one of the outcomes specified above, this event should be reported as serious).

### **11.1.3 Adverse reaction**

Any harmful and unintended response to a medication, including adverse reactions resulting from any use outside the terms of the marketing authorisation, abuse and error in the medication. There is a confirmed causal relationship with it.

## **11.2. Characteristics of an adverse event**

### **11.2.1. Severity**

See definition of Serious Adverse Event (11.2 Serious Adverse Event (SAE)).

### **11.2.2 Determination of causality**

The investigator is required to establish the causal link between the investigational drug and the adverse event (whether serious or not). A “reasonable possibility” is proposed to define cases where there are facts/evidence or arguments to suggest a causal link. The investigator will use clinical judgement to determine the relationship.

Alternative causes, such as the natural history of underlying diseases, concomitant treatment, other risk factors and the temporal link between the event and the investigational drug will be considered and investigated. The investigator will also consult the investigator's brochure for this evaluation.

There may be situations when an AE occurs where the investigator has minimal information to include in the initial report for the Sponsor. However, it is very important that the investigator always make a causality assessment for each event before submitting the data to the Sponsor. The investigator may change their opinion on causality based on information that arises during follow-up, so the report on the AE must be modified. Assessment of causality is one of the criteria that determine whether or not a case meets the reporting criteria for referral to the health authorities.

### **11.2.3 Expectability**

An unexpected adverse reaction is any that generates an unexpected adverse response that is related to the administration of the study drug at any dose and that is not consistent with the information in the investigator's brochure for the investigational product.

The sponsor will classify Adverse Reactions as expected or unexpected according to the Reference Safety Information included in the investigator's brochure.

#### **11.2.4 Severity**

The intensity of AEs will be evaluated using the CTCAE scale v. 5.0 (see Annex 6). If a CTCAE code does not exist, the following guide will be used:

Grade	Description
0	No adverse event
1	Mild; asymptomatic or mild symptoms; only requires clinical or symptomatic observation
2	Moderate; minimal, local or non-invasive intervention
3	Severe or medically important, but not immediately life-threatening; hospitalisation or extension of hospital stay
4	Life-threatening; requires urgent intervention
5	Death related to the adverse event

The grading of AEs is based on specific clinical criteria and requires evaluation by the site's investigator.

#### **11.2.5 Additional considerations**

Alterations in laboratory parameters (haematology, biochemistry or urine analysis) should be recorded as an AE or SAE, as well as abnormal results of other tests (such as ECGs, radiological tests, measurements of vital signs), including those that worsen from baseline values, which according to the investigator's medical and scientific criteria are considered clinically relevant.

In contrast, clinically significant changes in safety parameters associated with the study disease will not be classified as an AE or SAE unless the investigator determines that they are more serious than expected taking into account the patient's condition.

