## **6. STUDY DESIGN**

### **6.1. Design**

Multicentre, randomised clinical trial with three treatment arms.

Three cohorts of 9 patients will be included in the study. Each of the cohorts of 9 patients will include 3 arms (A, B, and C) at different dose levels with 3 patients in each arm, up to a maximum of 27 patients evaluable for safety.

The established dosage levels are as follows:

- Arm A) 1.5 mg of plitidepsin administered as a 1.5-hour infusion, once a day for 3 consecutive days.
- Arm B) 2.0 mg of plitidepsin administered as a 1.5-hour infusion, once a day for 3 consecutive days.
- Arm C) 2.5 mg of plitidepsin administered as a 1.5-hour infusion, once a day for 3 consecutive days.

ARM	Dosage level	Daily dose (mg)	Total dose (mg)
Arm A	1	1.5 mg x 3 days	4.5 mg
Arm B	2	2.0 mg x 3 days	6.0 mg
Arm C	3	2.5 mg x 3 days	7.5 mg

Recruitment will be sequential in each of the three arms. The first cohort of 3 patients in arms B and C (2.0 mg and 2.5 mg) will not open until the data have been analysed for the first 3 patients at the dose level immediately below (arms A or B) without observing any unacceptable toxicity, taking into account the data of the three patients included in each arm with a 12-day follow-up from the end of treatment (day +15 from the start of treatment).

When patients are to be included at more than one dose level (arm), patients will be randomised in a 1:1 or 1:1:1 ratio as appropriate.

The following criteria have been established to continue the inclusion of patients in the different arms:

- If 0-1 of the first three patients treated with the dose of 1.5 mg x 3 days experience any adverse event classed as grade 3 or higher within twelve days after administration of the last dose, three additional patients will be enrolled in the 1.5 mg arm and recruitment of the first three patients in the 2.0 mg arm will start. Recruitment in the 2.5 mg arm will be opened after it has been proven that only 0-1 of the three patients in the first cohort in the 2.0 mg arm have grade 3 or greater toxicity within twelve days of follow-up after administration of the last dose of 2.0 mg.
- 
- If 2 or more patients in any of the arms present an adverse event classed as grade 3 or higher, the sponsor will interrupt the recruitment of new patients and will jointly assess with the Spanish Agency of Medicines and Medical Devices whether or not to continue recruitment in that arm and in arms with a higher dose.

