### **12.4. Analysis of the primary endpoint**

The safety analysis will be performed in the safety population, that is, in patients who have received at least one dose of treatment. Patients will be analysed in the administered treatment arm.

Safety and tolerability analyses will be presented by treatment arm as well as by treatment arm according to age group (<65 years; ≥65 years). Adverse events will be coded using the latest version of the MedDRA dictionary and assessed using the NCI-CTCAE criteria v. 5.0.

The number and percentage of patients presenting the following ≥ grade 3 adverse events will be provided, according to the NCI-CTCAE criteria v. 5.0 at 3, 7, 15 and 31 days after the start of study treatment:

- Haematological
    - Neutropenia
    - Thrombopenia
    - Anaemia
    - Lymphopenia
  - Non-haematological
    - CPK increase
    - ALT and/or AST increase
    - Total bilirubin or direct bilirubin increase
    - Neurotoxicity
    - QT-QTc interval prolongation
  - Other ≥ grade 3 adverse events
- The number and percentage of patients in whom treatment cannot be completed and the reasons will be provided.
  - The number and percentage of patients with AEs and SAEs will be provided at 3, 7, 15 and 31 days.
  - The evolution of haematological and non-haematological parameters from the baseline visit on days 3, 7, 15 and 31 will be provided.

*CONFIDENTIAL*

- The number and percentage of patients with ECG abnormalities on days 1, 2, 3, 4, 5, 6, 7, 15 and 31 will be provided. Any alterations detected will be described in detail.

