Relationship between days of symptom evolution and disease severity.

Analysis of differences in inflammatory parameters (CRP, ferritin, transaminases, LDH) and hematological (lymphocytes) and level of viral load in patients according to the risk group of the FDA.

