11.6 Laboratory

Table 11.6.1 Shift in Hematology Parameters from Baseline to Greatest Change in Grade on Study for Combined Dose Groups

Parameter	Grade at Baseline	Grade Change per Patient on Study				
		0	1	2	3	Total
Anemia (hemoglobin)	0					
	1					
Leukopenia (leukocytes)	0					
	1					
	...					
.....						

This table will be also performed by age (<65 vs. >=65 year old) (11.6.1.1)

This table will be also performed by inflammatory parameters (11.6.1.2)

Laboratory table by pre&post amendment (13AUG2020) will be generated upon request. (11.6.1.3)

This table will be also performed by pre&post amendment (13AUG2020) (11.6.1.4)

Table 11.6.2 Shift in Chemistry Parameters from Baseline to Greatest Change in Grade on Study for Combined Dose Groups Percentages are shown for changes from baseline

Parameter	Grade at Baseline	Grade Change per Patient on Study				
		0	1	2	3	Total
ALT increased	0					
	1					
AP increased	0					
	missing					
AST increased	0					
	1					
.....					

This table will be also performed by age (<65 vs. >=65 year old) (11.6.2.1)

This table will be also performed by pre&post amendment(13AUG2020) (11.6.2.2)

Listing 11.6.3 Hematological laboratory parameters

Subject ID	Visit	Date	...(*)	change (%)	...()	change (%)
.....	Baseline					
	Day 3					
	...					

(*) Hematological parameters

Listing 11.6.4 Coagulation laboratory parameters

Subject ID	Visit	Date	...(*)	change (%)	...()	change (%)
.....	Baseline					

Subject ID	Visit	Date	...(*)	change (%)	...()	change (%)
	Day 3					
	...					

(*) Coagulation parameters

Table 11.6.5 Biochemical laboratory parameters

Subject ID	Visit	Date	...(*)	change (%)	...()	change (%)
.....	Baseline					
	Day 3					
	...					

(*) Biochemical parameters

Listing 11.6.6 Laboratory abnormalities reported in AE form

Dose Cohort	Subject id	AE	PT	SOC	Action	Relatedness	Study Day of Onset/Resolution

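### Protocol 11.2.5 lets disease-attributed or clinically irrelevant laboratory changes stay off the AE form, so the AE-based count of grade ≥3 laboratory toxicity by dose may be incomplete, and no visible SAP output replaces it

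*Protocol*

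**What the plan says.** **What becomes an AE.** Protocol 11.1.1 counts an untoward event, including an abnormal analytical result, "whether or not it is deemed to be related to the investigational products". Protocol 11.2.5 narrows this in two ways. Laboratory and other test abnormalities are to be recorded as AEs if they are ones "which according to the investigator's medical and scientific criteria are considered clinically relevant". The second limit concerns COVID-19 itself: "clinically significant changes in safety parameters associated with the study disease will not be classified as an AE or SAE". Excepted are changes judged worse than the patient's condition would lead one to expect.

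**What is counted.** Protocol 12.4 states: "The number and percentage of patients presenting the following ≥ grade 3 adverse events will be provided". Most of the named terms are laboratory events: neutropenia, thrombopenia, anaemia, lymphopenia, CPK, ALT/AST and bilirubin. No causality condition is attached. The interruption rule for the first 27 patients in Protocol 6.1 begins "If 2 or more patients in any of the arms present an adverse event classed as grade 3 or higher", again without one. The rule for opening the next dose level likewise refers to any such event. The extension rule in the same section differs: it counts only grade ≥3 events related to plitidepsin, with weekly reporting to the regulator of all reported grade ≥3 events whatever their cause.

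**Where the count comes from.** Protocol 12.5.2 takes the analysed AEs from the AE section of the case report form. The SAP keeps AE-form entries apart from the laboratory data: Listing 11.6.6 is titled "Laboratory abnormalities reported in AE form".

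**The concern.** The primary question is the toxicity profile at each dose. Section 11.2.5 places a judgement of relevance and cause ahead of recording, while the endpoint and the first-27 rules are written as if recording did not depend on cause. Masking does not apply (Protocol 7.4) and the trial is uncontrolled (Protocol 5.2), so that judgement is made with the dose known and with no comparator.

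Lymphopenia is the clearest case. SAP 8.1 examines lymphocytes against viral load and by COVID-19 severity group, so attribution to the disease is foreseeable. A grade 3 value put down to COVID-19 and not thought worse than expected would be missing from the grade ≥3 rows of SAP Tables 11.1.1 and 11.1.2, from Table 11.4.5 (which is meant to be regardless of relationship), from the first-27 recruitment count, and from the weekly reports in the extension.

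**Working it through.** **Step 1: do the laboratory outputs supply the missing count?** What is needed is grade ≥3, by parameter, by dose, from laboratory values.

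| SAP output | By dose? | By parameter? | Grade ≥3? |
|---|---|---|---|
| Tables 11.1.1 and 11.1.2, grade-change rows | Yes | No, pooled as haematological or non-haematological | No, ≥1 grade change |
| Tables 11.6.1 and 11.6.2, shift tables | No, doses combined | Yes | Recoverable from baseline grade plus change |
| 7.1, list of named terms | Yes | Yes | No, ≥1 grade change; source (AE form or laboratory) not stated |
| 7.2 and 9.5, laboratory listings | Arm shown | Yes | Values, not grades; baseline and days 3, 7, 15, 31 only |
| Table 11.4.5 | Yes | Yes, by preferred term | Yes, but AE-based |

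No visible laboratory output has all three properties. Protocol 10 schedules blood count and biochemistry daily on days 1 to 7 and on days 15 and 31, so a nadir on days 4 to 6 falls outside the 7.2 and 9.5 listings. Tables 11.4.6 to 11.4.13 are not in the copy of the SAP available here, so a further by-dose table cannot be excluded.

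**Step 2: how much could be missed?** The plan states no expected rate or undercount, so there is no figure to reproduce. Inputs:

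- True rate p of grade ≥3 lymphopenia. Protocol Annex 7 gives 18% (grade 3/4) in phase II studies. For the phase I daily ×5 study, Table 8 gives 1 + 1 + 3 + 2 + 2 = 9 of 19 overall, and 3/4, 2/3 and 2/4 at about 1.5, 2.0 and 2.5 mg, that is 7 of 11. The text below Table 8 gives three cases at 2.5 mg where the table gives two; the table agrees with the stated total of nine and is used.
- Share f of cases left off the AE form. This is an assumption, 0 to 75%; the documents give no figure.

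Recorded rate q = p(1 − f). Expected recorded cases per arm = 15q. Chance of at least two recorded among n patients = 1 − (1 − q)^n − nq(1 − q)^(n−1).

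For example, with p = 0.18 and f = 0.5, q = 0.09 and 15 × 0.09 = 1.35. For n = 9, 1 − 0.91^9 − 9 × 0.09 × 0.91^8 = 19.1%.

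| p | Quantity | f = 0 | 25% | 50% | 75% |
|---|---|---|---|---|---|
| 18% | Cases per 15 | 2.7 | 2.0 | 1.35 | 0.7 |
| 18% | ≥2 of 3 | 8.6% | 5.0% | 2.3% | 0.6% |
| 18% | ≥2 of 9 | 50.1% | 34.8% | 19.1% | 5.9% |
| 9/19 | ≥2 of 3 | 46.1% | 28.9% | 14.2% | 3.9% |
| 9/19 | ≥2 of 9 | 97.2% | 88.5% | 66.7% | 29.0% |
| 7/11 | ≥2 of 3 | 69.9% | 46.6% | 23.9% | 6.8% |

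These probabilities treat lymphopenia as the only event. The rules count any grade ≥3 AE, so the effect on the rules themselves would be smaller.

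**Step 3: transaminases.** Annex 7 reports no grade ≥3 AST or ALT in the 19 phase I patients. The exact 95% upper limit is 1 − 0.025^(1/19) = 17.6%. The daily-schedule data therefore show no effect comparable to lymphopenia, although Annex 7 does name liver-enzyme increase as a dose-limiting toxicity in the phase I programme.

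**The case against.** The strongest reply is that laboratory toxicity is already captured outside the AE form. Laboratory change from baseline is itself part of the primary endpoint. The cohort reviews in Protocol 12.5.3 repeat all the 12.4 analyses, laboratory evolution included, and are assessed with the regulator. SAP 14 promises individual laboratory listings, and SAP 15.3 plots lymphocytes and ALT by dose cohort. All of this stands, and it means the information is not lost. It does not supply a grade ≥3 count by parameter and dose.

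Second, the exemption keeps changes that are worse than expected. Protocol 7.2 excludes patients with lymphocytes below 800/µl, GOT/GPT above 3 × ULN, CPK above 2.5 × ULN or bilirubin above ULN, so many severe values would be new on study and could well be recorded. This stands as a reason why the omitted share may be low.

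Third, the phase I rates come from cancer patients on five daily doses, and seven of the nine with grade 3 lymphopenia already had grade 2 or 3 before treatment. They give a range, not a forecast.

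Fourth, counting every disease-related abnormality toward the interruption rule has a price. With nothing omitted, lymphopenia alone gives a 50.1% chance of two or more among nine patients at an 18% rate, and 97.2% at 9/19. Which events should trigger the rule is a genuine trade-off, and it is left open here.

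**Conclusion.** The point holds as an internal inconsistency and a gap in the planned outputs. Section 11.2.5 does not fit the cause-independent AE definition, the grade ≥3 component of the primary endpoint or the first-27 rules. The AE-based count of grade ≥3 laboratory toxicity by dose may be incomplete by an amount the documents do not allow one to estimate. The step 2 figures are illustrative and rest on an assumed omitted share and on rates from oncology patients.

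Four stronger readings are tempting and not supported:

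- That all the recruitment rules ignore cause. The extension rule, covering 18 of the 45 patients, requires relatedness.
- That lymphopenia and transaminase toxicity will be undercounted. No attribution share is given, the exemption has an exception, and the phase I data show 0 of 19 grade ≥3 transaminase events.
- That the omission cannot be undone. The laboratory values are collected, and grades can be derived from them.
- That events are removed selectively by dose. Unmasked attribution makes this possible, but nothing in the documents shows it.

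**What to change.** In Protocol 12.4 and SAP 7.1, add a table of CTCAE v5.0 grade ≥3 for neutropenia, thrombopenia, anaemia, lymphopenia, CPK, ALT/AST and bilirubin, derived from all recorded laboratory values, scheduled and unscheduled. Show it by parameter, dose and window (to days 3, 7, 15 and 31), with baseline grade, regardless of AE entry or attribution, and beside the AE-form count so that the difference is visible. State in SAP 7.1 whether its grade-change counts come from the AE form or from laboratory values.

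Protocol 6.1 (both the first-27 and the extension rules), 11.1.1 and 11.2.5 must be reconciled on whether disease-attributed laboratory findings are AEs and whether they count toward the recruitment rules.

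The cost is a small amount of programming on data already scheduled for collection. The derived grade ≥3 rates will include disease-related abnormalities, and without a control arm they cannot be separated from drug effect; showing baseline grade and the AE-form count alongside helps the reader to interpret them.
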